3.12. Interim Analyses

For reasons of futility (early observational evidence of poor efficacy of VGX-3100), the study has the potential to be stopped by the DSMB at any time. However, no formal interim analyses are planned, and the study is not designed to be stopped early based on evidence of efficacy.

4. STUDY ANALYSES

4.1. Subject Disposition

Subject disposition will be tabulated by treatment group and overall, and will include the number screened, the number of screen failures, the number randomized (in total and by stratum), the number treated by the highest number of doses received, the number in each subject population for analysis, the number that completed all study treatments and follow-up visit, the number who withdrew prior to completing the study treatment, the number who withdrew prior to completing all follow-up visits, and reason(s) for withdrawal. Reasons for not participating in study will also be summarized.

A by-subject data listing of study completion information including the reason for premature study withdrawal, if applicable, will be presented. Consent and randomization, inclusion/exclusion criteria, and study populations will also be provided in listings.

Relevant Output

| Table 14.1.1.1 Table 14.1.1.2 | Subject Enrollment and Disposition Summary of Primary Reasons for Not Participating in Study |
|----------------------------------|-------------------------------------------------------------------------------------------------|
| Listing 16.2.1.1 | Study Completion Status |
| Listing 16.2.1.2 | Consent and Randomization Information |
| Listing 16.2.2.1 | Inclusion/Exclusion Criteria and Eligibility |
| Listing 16.2.3.1 | Study Populations |
| Listing 16.2.3.2 | Randomized Subjects Who Were Never Vaccinated |
| Listing 16.2.3.3 | Subject Status Subgroups |
| | |

4.2. Demographics and Baseline Characteristics

Demographics and baseline characteristics will be summarized and presented by treatment group and overall. Age, height, weight, and BMI will be summarized using descriptive statistics (number of subjects, mean, SD, median, minimum, and maximum). The number and percentage of subjects in each randomization stratum, ethnicity category, race category, and country also will be presented. Results at screening for VIN category, HPV type, years of education, and type of insurance will also be presented.

Abnormal medical history will be summarized by term as collected on the electronic CRF. Prior vulvar disease, HPV diagnoses, and reproductive history will be presented in data listings as well as tobacco history and alcohol use.

No formal statistical comparisons between groups will be performed for demographics, baseline data, or medical history data. Data for each subject will also be provided in data listings.

Relevant Output

| Table 14.1.2.1A | Demographics and Baseline Characteristics (mITT/Safety Population) |
|------------------|--------------------------------------------------------------------|
| Listing 16.2.4.1 | Demographics and Baseline Disease Characteristics |
| Listing 16.2.4.2 | Abnormal Medical History |
| Listing 16.2.4.3 | Prior Vulvar Disease and HPV Diagnoses |
| Listing 16.2.4.4 | Reproductive System History |
| Listing 16.2.4.5 | Alcohol, Tobacco, and Recreational Drug Use |
| | |

4.3. Efficacy Evaluation

Efficacy analyses will be conducted using the mITT population. Supportive analyses of efficacy will be based on the PP population.

4.3.1. Primary Efficacy Endpoint

The primary efficacy endpoint is the combined outcome of histologic regression of vulvar HSIL and virologic clearance of HPV-16/18 at Week 48. Histologic regression is defined as no histologic evidence of vulvar HSIL (normal tissue or vulvar LSIL (VIN 1) or condyloma) at Week 48. Virologic clearance is defined as clearance of HPV 16 or 18 at Week 48. A subject achieves the primary outcome (i.e., is a "responder") if histologic regression and virologic clearance is observed at Week 48 and the subject did not receive any non-study related treatment for vulvar HSIL. A subject is a non-responder if there is histologic evidence of vulvar HSIL or vulvar carcinoma, or evidence of HPV-16/18, or subject received non-study related treatment for vulvar HSIL.

| Table 4-1: | Definition | of Responder | and Non-Responder |
|------------|------------|--------------|-------------------|
|------------|------------|--------------|-------------------|

| Responder | Non-Responder | | |
|-----------------------------------------------------------------------------------------------------------------------------|--------------------------------------------------------------------------------------------------------------|--|--|
| • Subject with no histologic evidence of vulvar HSIL | • Subject with histologic evidence of vulvar HSIL or vulvar carcinoma at evaluation | | |
| AND | OR | | |
| Subject with no evidence of HPV-16 or HPV-18 in vulvar tissue at evaluation AND | Subject with evidence of HPV-16 or HPV-18 in vulvar tissue at evaluation OR | | |
| • Subject did not receive any non-study related treatment for vulvar HSIL | • Subject who received non-study related treatment for vulvar HSIL | | |
| Note: The efficacy time frame is defined by samples obtained any time starting from 14 days prior to the protocol-specified | | | |

target date of Week 48. The first such sample determines the histology endpoint. The most recent HPV clearance result prior to time of the histology sample within the time frame determines the HPV clearance endpoint.

The number and percentage of subjects with response for the primary endpoint will be presented for each treatment group and compared to historical control separately. A 1-sided p-value and corresponding 2-sided 95% CI using Clopper-Pearson exact binomial methods will be presented for each comparison to prove superiority over historical control. Superiority of VGX-3100 alone or in combination with imiquimod will be declared if 1-sided p-value is <0.025 and the lower end of the CI is greater than 0.02. The primary efficacy will be analyzed separately based on qualifying lesions present at baseline and for all lesions regardless of presence at baseline.

Relevant Output

| Table 14.2.1.1A | Primary Efficacy Analysis: Incidence of Histologic Regression and |
|------------------|-------------------------------------------------------------------|
| | Virologic Clearance at Week 48 (mITT Population) |
| Table 14.2.1.1B | Primary Efficacy Analysis: Incidence of Histologic Regression and |
| | Virologic Clearance at Week 48 (PP Population) |
| Listing 16.2.6.1 | Primary Efficacy Results |

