1.2. Study Design

1.2.1. Synopsis of Study Design

HPV-201 is a Phase 2, randomized, open-label efficacy study of VGX-3100 (DNA plasmids encoding E6 and E7 proteins of HPV types 16 and 18) administered by IM injection followed by EP delivered with CELLECTRA[™] 2000 alone or in combination with imiquimod in adult women with histologically confirmed vulvar HSIL associated with HPV-16/18. Approximately 36 subjects will be enrolled. Twenty-four subjects will receive VGX-3100 alone and 12 subjects will receive VGX-3100 and topical imiquimod treatment.

To be eligible for the study, subjects must sign consent to participate and have a vulvar punch biopsy/biopsies of approximately 4 mm with lesion remaining, and photographs of the acetowhite vulvar lesion(s) at the time of screening. In the case of multifocal disease, the 2 lesions that potentially contain the most advanced disease, as judged by the Investigator, should be chosen for biopsy using vulvoscopy and documented using standardized high-resolution photography with a digital single-lens reflex (SLR) camera on the case report form (CRF). Biopsy slides will be sent to a PAC for evaluation prior to enrollment. In order to be eligible for enrollment, the PAC must assign the diagnosis of vulvar HSIL based on the biopsy sample(s). Subjects must also have a vulvar specimen test positive for HPV genotype 16 and/or 18 to be eligible for participation in the study.

All eligible subjects who consent to participate in the study will receive at least 4 doses of 6 mg of VGX-3100 administered by IM injection followed by EP. Subjects randomized to the VGX-3100 with imiquimod arm will apply imiquimod 5% cream to the vulvar lesion beginning in the evening on Day 0, and will continue to apply treatment 3 times per week for 20 weeks (inclusive of administration in the evening of VGX-3100 dosing).

Subjects will be placed into the following subgroups depending on status of biopsies performed at Week 48, Week 74, and Week 96:

- Subgroup A: Subjects having no HSIL and no visible lesions
- Subgroup B: Subjects having no HSIL but with a visible lesion
- Subgroup C: Subjects having HSIL with >25% and <100% lesion area reduction from baseline
- Subgroup D: Subjects having HSIL with 0-25% lesion area reduction from baseline
- Subgroup E: Subjects having HSIL and any increase in lesion area from baseline or worsening to cancer

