1.2.2. Randomization Methodology

Subjects are randomized by Y-Prime, Inc. to VGX-3100 alone or VGX-3100 in combination with imiquimod in a 2:1 ratio using a central randomization algorithm. Randomization will be done in a stratified manner according to (a) recurrent disease at screening (0 vs. 1 or more recurrences), (b) multifocal disease (1 vs. 2 or more lesions at screening), (c) Body Mass Index (BMI) category (≤ 25 vs. ≥ 25 kg/m2), and (d) age category (≤ 45 years vs. ≥ 45 years).

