- ³ Screening 12-lead ECG, complete blood count (CBC), serum electrolytes, blood urea nitrogen (BUN), creatinine (Cr), glucose, ALT, CPK and urinalysis performed within 45 days prior to first dose administration.
- ⁴ Negative spot urine pregnancy test is required at screening and prior to each study treatment, vulvoscopy and biopsy/surgical excision.
- ⁵ At least 34 mL (4 x 8.5 mL yellow (ACD) tubes) whole blood and 4 mL serum per time point. At least 68 mL whole blood and 8 mL serum should be collected prior to first dose. One additional 8.5 mL yellow (ACD) tube to be collected at Day 0, Week 15 and 48 for microRNA analysis.
- ⁶ At least 51 mL [6 x 8.5 mL yellow (ACD) tubes] whole blood and 4 mL serum should be collected at Week 27.
- ⁷ Cervical colposcopy will be performed once at Day 0, and once at Week 96. For subjects completing the study at Week 78, the repeat cervical colposcopy will be performed at Week 74 or the discharge visit.
- ⁸ HPV genotyping and Pap smears are performed on the same ThinPrep® cervical specimen.
- ⁹ An additional visit may be scheduled to perform vulvoscopy if worsening of disease is suspected. Biopsies should not be performed at any visit other than at entry (Screening), Week 48, Week 74 and Week 96 for subjects in Subgroups C and D prior to Amendment 5.0 unless the Investigator suspects invasive cancer. All biopsy samples and/or excision samples obtained prior to or at the subjects final discharge visit (if not a phone visit) must be sent to the PAC for review.
- ¹⁰ Photography of the acetowhite stained qualifying lesion(s) must be performed prior to and after biopsy, and at all vulvoscopy examinations. If a pre-biopsy digital photograph is not available for a historical biopsy sample at screening, a post biopsy photo will be sufficient. Additionally, standardized high resolution digital photographic imaging should be obtained during examinations of the vagina if lesions are identified, for documentation.
- ¹¹ Tissue specimen from all excised tissue obtained prior to or at the subjects in-person discharge visit must be reviewed by the PAC and will be sent to the central laboratory for HPV testing. All lesions will be biopsied at Week 48, 74, and 96 (as applicable), per Amendment 5.0.
- ¹² HPV genotyping is performed on vulvar tissue specimen using a PCR based assay.

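### The first-sample note to Table 4-1 conflicts with the subject-level responder definition when several lesions are biopsied at Week 48, and no rule combines them

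*SAP*

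**What the plan says.** The note to Table 4-1 (SAP 4.3.1) sets a time frame of "samples obtained any time starting from 14 days prior to the protocol-specified" Week 48 target date, with no closing date. It then states: "The first such sample determines the histology endpoint". The next sentence refers to one histology sample again: "The most recent HPV clearance result prior to time of the histology sample within the time frame determines the HPV clearance endpoint".

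Other parts of the SAP lead one to expect several samples per subject:

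- SAP 1.2.4, Table 1-1, footnote 11: "All lesions will be biopsied at Week 48, 74, and 96 (as applicable), per Amendment 5.0".
- SAP 1.2.1, on screening biopsies: "In the case of multifocal disease, the 2 lesions that potentially contain the most advanced disease" are chosen.
- SAP 1.2.2 stratifies randomization by "multifocal disease (1 vs. 2 or more lesions at screening").

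Two statements in SAP 4.3.1 work at subject level over lesions. The non-responder column of Table 4-1 reads "Subject with histologic evidence of vulvar HSIL or vulvar carcinoma at evaluation". The paragraph after the table says the primary endpoint is to be "analyzed separately based on qualifying lesions present at baseline and for all lesions regardless of presence at baseline". SAP 4.3.2 carries the same two-way split to most secondary and exploratory binary endpoints.

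**The concern.** A multifocal subject can have one lesion without HSIL and another with HSIL, both biopsied at the Week 48 visit. Under the literal note, histology is decided by whichever sample is first. Under the table, the subject is a non-responder. Both rules govern the primary endpoint, and the SAP does not rank them or say how several samples are combined. For biopsies taken on one day, it does not define which is first.

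The possible error has one direction. A subject clear in every lesion is also clear in the first, so relative to the any-lesion definition the literal rule can add responders but never remove them. Each arm is compared with a fixed 2% historical rate (SAP 3.1, 4.3.1), so no concurrent arm scored the same way offsets the excess.

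**Working it through.** **1. The passages side by side.** Take a subject with lesion 1 = no HSIL and lesion 2 = HSIL, both sampled at Week 48, HPV-16/18 clear and no non-study treatment.

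| Rule in the SAP | Result |
|---|---|
| Note, lesion 1 taken as first | regressed, responder |
| Note, lesion 2 taken as first | not regressed, non-responder |
| Table 4-1, non-responder column | non-responder |
| Analysis of all lesions | needs both results; no combining rule stated |

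**2. The plan's own figures.** Inputs: arms of 24 and 12 (SAP 1.2.1); 90% evaluable, true rates 20% and 28%, historical rate 2%, one-sided 0.025 (SAP 3.1). Evaluable n = 0.9 × 24 = 21.6 and 0.9 × 12 = 10.8. The exact rule is the smallest r with P(X ≥ r | n, 0.02) < 0.025.

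| Arm | n | r | Error at 2% | Power |
|---|---|---|---|---|
| VGX-3100 alone | 21 / 22 | 3 | 0.008 / 0.009 | 82.1% / 84.6% |
| With imiquimod | 10 / 11 | 2 | 0.016 / 0.020 | 81.7% / 85.8% |

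The stated 80% power is reproduced as at least 80%. The Clopper-Pearson lower limits at r are 0.029 (3 of 22) and 0.023 (2 of 11), both above 0.02, so the two parts of the success rule agree. With cut-offs this low, one misclassified subject turns 2 of 22 into 3 of 22, or 1 of 11 into 2 of 11, and so changes the conclusion for that arm.

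**3. Illustration of size (assumptions, not SAP figures).** Assume two lesions per multifocal subject, a multifocal share m, and within-subject correlation rho. Let p be the chance that one given lesion is clear. Hold the true subject-level rate at 2%:

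p² + rho × p(1 − p) = 0.02.

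Scored on one lesion, the overall rate is (1 − m) × 0.02 + m × p. Example with rho = 0.5: p² + p − 0.04 = 0, so p = (−1 + √1.16)/2 = 0.0385. With m = 0.5 the rate is 0.5 × 0.02 + 0.5 × 0.0385 = 0.029.

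| rho | p | Rate, m = 30% / 50% | Error, n=22, r=3 | Error, n=11, r=2 |
|---|---|---|---|---|
| 0.75 | 2.6% | 2.2% / 2.3% | 0.012 / 0.014 | 0.023 / 0.026 |
| 0.5 | 3.9% | 2.6% / 2.9% | 0.018 / 0.025 | 0.031 / 0.040 |
| 0.25 | 6.7% | 3.4% / 4.3% | 0.037 / 0.068 | 0.052 / 0.080 |
| 0 | 14.1% | 5.6% / 8.1% | 0.12 / 0.26 | 0.12 / 0.22 |

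**4. Check without the lesion model.** Add a share f of false responders directly to the true 2%. At f = 1% the error is 0.024–0.027 (n = 21–22) and 0.035–0.041 (n = 10–11). At f = 2% it is 0.050–0.056 and 0.058–0.069.

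**The case against.** The best defence is that the note concerns time and does not choose among lesions. It refers back to a window that never closes, so picking the first sample naturally means taking the earliest sampling occasion over a later biopsy or excision. On that reading, same-day biopsies are all first. Table 4-1 already makes any HSIL at evaluation a non-response, and separate analyses of qualifying and of all lesions make sense only if results are combined within a subject. This may well be what was meant, but the note says sample, repeats the singular in its HPV sentence, and is nowhere reconciled with the table.

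The figures are also open to challenge. The highest errors need zero correlation between lesions in the same treated woman and 50% multifocal disease. At rho 0.75 the VGX-3100-alone arm stays below 0.025 and the imiquimod arm is at about that level. The model scores the whole composite, HPV included, on the first lesion; if HPV is judged over all vulvar tissue, false responders are fewer. Because footnote 11 attributes all-lesion biopsy to Amendment 5.0, subjects biopsied earlier may have fewer samples. All of this stands and limits the size of the problem, but the conflict remains.

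A reader might also infer that a lesion biopsied some days after the first would be discarded. The SAP gives no basis for expecting this: Table 1-1 has one Week 48 visit, and footnote 9 confines biopsies to scheduled time points unless invasive cancer is suspected.

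**Conclusion.** The point holds as an unreconciled conflict within section 4.3.1, together with a missing rule for combining lesions. It should be settled before database lock, because the trial is open-label and the choice could otherwise be made with results in view.

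A reader might go further and infer that the plan turns the primary endpoint into a one-lesion endpoint with an inflated error rate. The SAP does not support that. The table and the lesion-set analyses point to an any-lesion reading, and the inflation arises only if the note is applied literally.

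Under the literal reading the direction is certain (responders can only be added), but the size is not known. Over the assumed range, one-sided error is 0.012 to 0.26 for 22 evaluable subjects and 0.023 to 0.22 for 11, against 0.009 and 0.020 with no misclassification. It would be smaller if HPV is judged over all vulvar tissue. These figures rest on an assumed multifocal share, two lesions per multifocal subject and an assumed correlation, none of which the SAP gives.

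**What to change.** Replace the histology sentence in the note with: *The first sampling occasion (visit) in the time frame determines the histology endpoint; HSIL or carcinoma in any sample from that occasion, among the lesions in the analysed set (qualifying lesions, or all lesions), makes the subject a non-responder.*

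Rewrite the HPV sentence to match, since it now depends on a single histology sample: *HPV-16/18 detected in any vulvar tissue sample of the analysed set at that occasion means not cleared.*

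Apply the same rule to the Week 74 and Week 96 endpoints in section 4.3.2.

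The cost is a few lines of SAP text and one derivation rule. No new data are needed, as footnotes 9 and 11 already send the biopsy samples for adjudication and the tissue for HPV testing. The reported response rate may be slightly lower than under the literal note.

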- ¹³ Potential dosing, post-treatment assessment, and distribution of the Participant Diary at Week 52 and Week 78 is applicable for partial responders only. Partial responders who reach Week 78 after Amendment 5.0 will not be offered a 6th dose.
- ¹⁴ Subjects will take home imiquimod plus an imiquimod dosing log to document their use of imiquimod. Administration of imiquimod begins on Day 0.
- ¹⁵ A phone call will be used to review the Participant Diary (PD) with subject within 8-14 days following dose 1 and 2. The patient will be expected to bring the PD to the next visit for review.
- ¹⁶ PRO measures (SF-36v2TM, EQ-5D-5L, WOMAN-PRO) plus 2 additional questions will be assessed as described in protocol Section 6.8.

- 1.2.5. Efficacy, Immunology, and Safety Parameters
- 1.2.5.1. Efficacy Parameters

The primary efficacy endpoint is the combined response outcome of histopathologic regression of vulvar HSIL and virologic clearance of HPV-16/18 in vulvar tissue at Week 48.

The secondary efficacy endpoints include the following:

- Histopathological regression is defined as no histologic evidence of vulvar HSIL at Week 48.
- Virologic clearance is defined as no evidence of HPV-16/18 at Week 48 in vulvar tissue samples.
- Proportion of subjects with no histologic evidence of vulvar HSIL or no evidence of HPV-16/18 at Week 48 in vulvar tissue samples (i.e. collected via biopsy or excisional treatment).
- Proportion of subjects with no evidence of vulvar HSIL, no evidence of vulvar LSIL (VIN1), and no evidence of condyloma on histology (i.e. biopsies or excisional treatment) at the Week 48 visit.
- Proportion of subjects with no progression of vulvar HSIL to vulvar cancer from baseline to Week 48 visit.
- Percent reduction in the cumulative surface area of qualifying acetowhite vulvar lesion(s) as determined by the quantitative analysis of standardized pre-biopsy photographic imaging of qualifying lesion(s) at Week 48 compared to baseline. Results will be classified as:
 - No clinically significant lesion resolution (reduction in lesion area of 0-25%),
 - Partial lesion area resolution (>25% and <100% reduction),
 - Complete lesion resolution (no visible lesion).

Exploratory efficacy endpoints include the following:

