3.11. Visit Windows

It is expected that all visits should occur according to the protocol schedule. All data will be tabulated per the evaluation visit as recorded on the CRF even if the assessment is outside of the visit window. In data listings, the relative day of all dates will be presented.

The efficacy time windows for histologic regression and virologic clearance are defined by samples obtained any time starting from 14 days prior to the protocol-specified target date of visit.

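### The timing rule for the HPV half of the primary endpoint cannot be met by the tissue result that Table 4-1 requires, so potential responders cannot be classified as written

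*SAP*

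**What the plan says.** All references are to the SAP.

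- **Window (Section 3.11).** Histologic regression and virologic clearance use "samples obtained any time starting from 14 days prior to the protocol-specified target date of visit". No upper limit is given.
- **Histology (Section 4.3.1, note to Table 4-1).** "The first such sample determines the histology endpoint".
- **HPV (same note).** "The most recent HPV clearance result prior to time of the histology sample within the time frame determines the HPV clearance endpoint". No specimen type is named.
- **Responder row of Table 4-1.** "Subject with no evidence of HPV-16 or HPV-18 in vulvar tissue at evaluation". The non-responder row also refers to vulvar tissue.
- **Endpoint list (Section 1.2.5.1).** "Virologic clearance is defined as no evidence of HPV-16/18 at Week 48 in vulvar tissue samples".
- **Source of the tissue result (Table 1-1, footnote 12).** "HPV genotyping is performed on vulvar tissue specimen using a PCR based assay". Footnote 11 says that excised tissue "must be reviewed by the PAC and will be sent to the central laboratory for HPV testing".
- **Schedule (Table 1-1).** Biopsy and vulvar HPV genotyping are marked at the same four visits: Screening and Weeks 48, 74 and 96. Footnote 9 bars biopsies at other visits unless the investigator suspects invasive cancer.
- **Prose definition (Section 4.3.1).** "Virologic clearance is defined as clearance of HPV 16 or 18 at Week 48".

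**The concern.** The note and the table cannot both be followed. The note wants an HPV result that comes before the histology sample and inside the window. The table wants a tissue result, and tissue is obtained only by taking the biopsy or excision that is the histology sample. The rule governs half of the composite primary endpoint.

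A programmer working from the note has two courses. One is to find no qualifying tissue result for a subject whose histology has regressed. That subject then has no derivable primary endpoint, and the mITT definition in Section 2.1 keeps only subjects who have the endpoint being analysed. The other is to depart from the written rule, by using the same-day tissue result or by looking for some other HPV result that precedes the biopsy. The trial is open-label (Section 1.2.3), so the choice should not be left until the endpoint is derived.

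**Working it through.** **1. Can any tissue HPV result satisfy the note?** Take each possible source of tissue in turn.

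| Tissue source | Inside the window? | Before the histology sample? |
|---|---|---|
| Screening biopsy | No; the window opens 14 days before the Week 48 target | Yes |
| Week 48 biopsy or excision | Yes | No; it is the histology sample |
| Unscheduled biopsy for suspected cancer, after the window opens and before the Week 48 biopsy | Yes | No; as the first sample it becomes the histology sample |
| Week 74 or 96 tissue | Yes, since no upper limit is given | No; later than any Week 48 sample, and itself the histology sample if there is none |

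No row meets both conditions.

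**2. Which subjects need the HPV result?** The non-responder criteria in Table 4-1 are joined by OR. Residual HSIL, carcinoma, or non-study treatment for HSIL each settles the outcome without HPV. What remains is the group with histologic regression and no non-study treatment. Every potential responder is in it. If those subjects were dropped for lack of an endpoint, only non-responders would remain. The SAP gives no histology-only regression rate, so the size of the group cannot be computed from the document.

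**3. Could a non-tissue result fit the note?** Table 1-1 schedules vulvar swabs, an oral rinse, vaginal and intra-anal swabs, and a cervical ThinPrep sample at Week 48. The SAP does not give their order relative to the biopsy. If one were taken first, it would satisfy the words of the note but not the table.

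**4. How many responders decide an arm?** Inputs are from Sections 1.2.1 and 3.1: arms of 24 and 12; 90% evaluable, so 0.9 × 24 = 21.6 and 0.9 × 12 = 10.8; response rates 20% and 28% against 2%; 1-sided 0.025 per arm; 80% power. For X ~ Binomial(n, p), take the smallest r with P(X ≥ r | p = 0.02) < 0.025. Power is P(X ≥ r) at the assumed response rate.

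| Arm | n | r | Exact 1-sided alpha | Power |
|---|---|---|---|---|
| VGX-3100 alone, 20% | 21 | 3 | 0.0081 | 82.1% |
| VGX-3100 alone, 20% | 22 | 3 | 0.0093 | 84.6% |
| With imiquimod, 28% | 10 | 2 | 0.0162 | 81.7% |
| With imiquimod, 28% | 11 | 2 | 0.0195 | 85.8% |

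The stated 80% is reproduced as a minimum. The lower Clopper-Pearson limits at these counts (0.0305, 0.0291, 0.0252 and 0.0228) also exceed 0.02, as Section 4.3.1 requires.

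**5. Effect of one reclassified subject.**

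- n = 22: 3 responders give p = 0.009. With 2, p = 1 − 0.98²² − 22 × 0.02 × 0.98²¹ = 0.071.
- n = 11: 2 responders give p = 0.0195. With 1, p = 1 − 0.98¹¹ = 0.199.

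**The case against.** The best defence is that the intent is plain. A literal reading would make the planned analysis impossible, so a sensible programmer would read the note as at or before the histology sample and use the tissue result from that biopsy. That is probably what was meant, but the text does not say it, and a primary-endpoint derivation should not rest on inferred intent.

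Four stronger readings are tempting, and the SAP does not support them:

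- **That every subject is affected, or the mITT population is emptied.** Subjects with residual HSIL, carcinoma or non-study treatment are classifiable without HPV. The separate histologic regression endpoint does not use the HPV rule.
- **That the plan substitutes a swab for tissue.** The primary objective (Section 1.1.3.1), the endpoint list, Table 4-1 and Section 4.3.2 all specify vulvar tissue, and the listings separate tissue from swab results. The note leaves room for a non-tissue result by naming no specimen; it does not call for one.
- **That the 16 or 18 sentence is a second, looser definition.** Taken alone, it could be read as met when a subject with both types clears one. The non-responder sentence in the same paragraph and Table 4-1 override it: evidence of either type is a non-response. It is loose wording only.
- **That the p-value contrast measures this defect.** It shows how fragile small arms are to any single reclassification. The SAP gives no rate of swab–tissue disagreement or of dual infection, so the number of subjects who would be misclassified is unknown.

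**Conclusion.** The defect is real but narrow. The note to Table 4-1 sets a timing condition that no tissue HPV result can meet, so read literally the primary endpoint cannot be derived for subjects with histologic regression and no non-study treatment. Use of a non-tissue result is a possibility left open by the note, not a stated rule. The conclusion rests on reading the note's words strictly and on tissue HPV being measured on the biopsy or excision specimen, as the schedule and footnotes indicate. No planned figure is wrong on this account. The size is the decision threshold: 3 responders of 21–22, or 2 of 10–11, assuming 90% of each arm is evaluable. One misclassified subject can therefore change an arm's conclusion. The sentence should be corrected before the endpoint is derived.

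**What to change.** Replace the HPV sentence in the note to Table 4-1 with:

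> The HPV endpoint is the HPV-16/18 genotyping result from the same vulvar tissue sample(s) that determine the histology endpoint. Within the lesion set being analysed (qualifying baseline lesions, or all lesions), all such samples must be negative for both types. Swab and other non-tissue results are not used.

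The restriction to the lesion set is needed because Section 4.3.1 analyses the primary endpoint separately for qualifying baseline lesions and for all lesions. A blanket requirement that every sample be negative would let a positive new lesion fail the qualifying-lesion analysis.

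Apply the same rule to the tissue clearance endpoints at Weeks 48, 74 and 96 in Section 4.3.2. As a minor alignment, reword the prose definition of virologic clearance in Section 4.3.1 so that it requires neither HPV-16 nor HPV-18 to be found in vulvar tissue, as Table 4-1 does.

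The cost is SAP wording and one derivation rule. No new data, samples or visits are needed.
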